8.2.3.2. Tumor Tissue

Collection of the following tumor tissue samples is mandatory for all patients:

- newly obtained biopsy specimens taken from the primary tumor lesion pre- and post-olatumab monotherapy treatment will be collected. The pretreatment tissue biopsy is to be performed within the screening period. The posttreatment tissue biopsy is to be performed after completion of the lead-in cycle of olatumab monotherapy and prior to

the initiation of combination therapy (Cycle 2). Refer to [Attachment 1](#) for additional details. If clinically feasible, the biopsies should be taken from the same primary tumor lesion.

Collection of the following tumor tissue samples is optional for all patients:

- biopsy specimen collected at the end of the patient's study treatment. Refer to [Attachment 1](#) for additional details. If clinically feasible, this biopsy should be taken from the same primary tumor lesion.
- tumor tissue from any post-therapy surgical resection may also be collected and provided. While this specimen is optional, it is expected this sample will be sent for analysis.

Sites should examine samples to determine adequacy of tumor tissue using their local laboratory procedures prior to the first dose of olaratumab monotherapy and again prior to the first dose of combination therapy. If additional tumor biopsies are collected as part of clinical care, they should be submitted, along with local pathology reports, for further analysis.

Details for the handling and shipping of the tumor tissue will be provided by Lilly in a separate document. The tissue samples will be obtained using appropriate method. Tumor tissue should be submitted as a newly acquired excisional or core needle (minimum 18 gauge) biopsy in formalin (10% neutral buffered). Cytological or fine-needle aspiration specimens are not acceptable. Due diligence should be used to make sure that tumor sample (not a normal adjacent or a tumor margin sample) is provided. Pathology reports accompanying tissue may also be requested. The reports must be coded with the patient number. Personal identifiers, including the patient's name and initials, must be removed from the institutional pathology notes prior to submission.

Collected tumor samples will be used for research on the drug targets, disease process, pathways associated with STS and/or cancer-related conditions, immune cells/immune and tumor microenvironment functioning within the disease state and/or cancer-related conditions, MOA of olaratumab or doxorubicin, and/or research methods or in validating diagnostic tools or assay(s) related to cancer. The primary analysis of these tumor tissue samples will be focused on the assessment of expression level change of PDGFR α , PDGFR β , and canonical ligands (*PDGF A*, *B*, *C*, and *D*) pre- and post-olaratumab monotherapy treatment. The relationship of baseline expression and expression level changes from baseline of these markers will also be evaluated. In addition, as a part of exploratory analysis mutation profiling, gene expression, sequencing and/or IHC may be performed on these tissue samples to evaluate changes in immune cell infiltration, activation, modulation, microenvironment and changes in stromal and tumor biology in response to study treatment. This may include evaluation of biomarkers related to, but not limited to, PD1 ligand and tumor infiltrating lymphocytes on tumor and stroma cells.

The samples will be coded with the patient number and stored for up to a maximum 15 years after the last patient visit for the study at a facility selected by the sponsor. The samples and any data generated from them can only be linked back to the patient by investigator site personnel. The duration allows the sponsor to respond to regulatory requests related to the study drug.

Samples will be destroyed according to a process consistent with local regulation.

8.2.3.3. Imaging Studies

A pre- and post-olaratumab monotherapy positron emission tomography (PET) scan will be collected for exploratory analyses at times specified in [Attachment 1](#). Positron emission tomography scan analyses measure tumor metabolic activity. Associations between PET scan findings, tissue biomarkers, and CTCs will be investigated in this study.

8.2.4. Samples for Pharmacogenetics

There is growing evidence that genetic variation may impact a patient's response to therapy. Variable response to therapy may be due to genetic determinants that impact drug absorption, distribution, metabolism, and excretion, the mechanism of action of the drug, the disease etiology and/or the molecular subtype of the disease being treated. Therefore, where local regulations and ERBs allow, a blood sample will be collected for pharmacogenetic analysis ([Attachment 1](#)).

In the event of an unexpected AE or the observation of unusual response, the pharmacogenetic biomarker samples may be genotyped and analysis may be performed to evaluate a genetic association with response to olaratumab and/or doxorubicin. These investigations may be limited to a focused candidate gene study or, if appropriate, genome-wide analysis may be performed to identify regions of the genome associated with the variability observed in drug response. The pharmacogenetic biomarker samples will only be used for investigations related to disease and drug or class of drugs under study in the context of this clinical program. They will not be used for broad exploratory unspecified disease or population genetic analysis.

The samples will be coded with the patient number and stored for up to a maximum 15 years after the last patient visit for the study at a facility selected by the sponsor. The samples and any data generated from them can only be linked back to the patient by investigator site personnel. The duration allows the sponsor to respond to regulatory requests related to the study drug.

Samples will be destroyed according to a process consistent with local regulation.

8.2.5. Samples for Immunogenicity Research

Blood samples for IG testing will be collected to determine antibody production against olaratumab. Refer to [Attachment 4](#) for details. Immunogenicity will be assessed by a validated assay designed to detect anti-drug antibodies in the presence of olaratumab. Antibodies may be further characterized and/or evaluated for their ability to neutralize the activity of olaratumab.

Samples may be stored for a maximum of 15 years following last patient visit for the trial at a facility selected by the sponsor to enable further analysis of immune responses to olaratumab. The duration allows the sponsor to respond to regulatory requests related to olaratumab.

8.3. Efficacy Evaluations

A secondary objective of the study is to document any antitumor activity. Refer to [Attachment 1](#) for details regarding the timing of specific efficacy measures.

Tumor assessments will be performed for each patient at the times shown in [Attachment 1](#) until documented progression for patients with CR, PR, or SD, and/or for patients who have discontinued study treatment due to toxicity or reasons other than PD. Imaging requirements include computed tomography (CT) scan or magnetic resonance imaging (MRI) of chest, abdomen, and pelvis and other areas, as clinically indicated.

Computed tomography scans, including spiral CT, are the preferred methods of measurement.

The exploratory PET Scan performed pre and post Cycle 1 will not be used to determine efficacy.

The CT portion of a PET-CT scan may be used as a method of response assessment if the site can document that the CT is of identical diagnostic quality to a diagnostic CT (with IV and oral contrast). A PET scan alone or as part of a PET-CT may be performed for additional analyses, but cannot be used to assess response according to RECIST.

The method of tumor assessment used at baseline must be used consistently throughout the study. Patients will be evaluated for response according to RECIST v1.1 guidelines (Eisenhauer et al. 2009), as outlined in [Attachment 8](#).

8.4. Procedure/Sampling Compliance

Every attempt will be made to enroll patients who have the ability to understand and comply with instructions. Noncompliant patients may be discontinued from the study.

The collection times of safety assessments, PK samples, and efficacy measurements are given as targets to be achieved within reasonable limits. The scheduled time points may be subject to minor alterations; however, the actual collection time must be correctly recorded on the eCRF.

The scheduled collection times may be modified by the sponsor based on analysis of the safety and PK information obtained during the study. Any major modifications that might affect the conduct of the study, patient safety, and/or data integrity will be detailed in a protocol amendment.

9. Data Management Methods

9.1. Data Quality Assurance

To ensure accurate, complete, and reliable data, Lilly or its representatives will do the following:

- provide instructional material to the study sites, as appropriate
- sponsor start-up training to instruct the investigators and study coordinators. This session will give instruction on the protocol, the completion of the CRFs, and study procedures
- make periodic visits to the study site
- be available for consultation and stay in contact with the study site personnel by mail, telephone, and/or fax
- review and evaluate CRF data and/or use standard computer edits to detect errors in data collection.
- conduct a quality review of the database.

In addition, Lilly or its representatives will periodically check a sample of the patient data recorded against source documents at the study site. The study may be audited by Lilly or its representatives and/or regulatory agencies at any time. Investigators will be given notice before an audit occurs.

To ensure the safety of participants in the study, and to ensure accurate, complete, and reliable data, the investigator will keep records of laboratory tests, clinical notes, and patient medical records in the patient files as original source documents for the study. If requested, the investigator will provide the sponsor, applicable regulatory agencies, and applicable ERBs/institutional review boards (IRBs) with direct access to the original source documents.

9.2. Data Capture Systems

9.2.1. Case Report Form

An electronic data capture system will be used in this study. The site maintains a separate source for the data entered by the site into the sponsor-provided electronic data capture system.

Case report form data will be encoded and stored in a clinical trial database.

For data handled by a data management third-party organization (TPO), CRF data and some or all data that are related will be managed and stored electronically in the TPO system. Subsequent to the final database lock, validated data will be transferred to the Lilly data warehouse, using standard Lilly file transfer processes.

For data handled by the sponsor internally, CRF data and some or all data that are related will be managed by the sponsor and stored electronically in the sponsor's system.

9.2.2. Ancillary Data

Data managed by a central vendor will be stored electronically in the central laboratory's database system. Data will subsequently be transferred from the central vendor to the Lilly clinical laboratory results modernization (CLRM) system.

Bioanalytical data will be stored electronically in the bioanalytical laboratory's database. Data will subsequently be transferred from the bioanalytical laboratory to the Lilly CLRM system.

Digital ECGs will be electronically transmitted to a central ECG laboratory designated by Lilly. The central ECG laboratory will perform a basic quality control check (for example, demographics and study details) and will then store the ECGs in a database. At a future time, the stored ECG data may be overread at the central ECG laboratory for further evaluation of machine-read measurements or to meet regulatory requirements.

Data from complaint forms submitted to Lilly will be encoded and stored in the global product complaint management system.

10. Data Analyses

10.1. General Considerations

Statistical analysis of this study will be the responsibility of Lilly.

The analyses for this study will mostly be descriptive. For continuous variables, summary statistics will include the number of patients, mean, median, standard deviation, minimum and maximum. Categorical endpoints will be summarized using the number of patients, frequency, and percentages. For time-to-event endpoints, the Kaplan-Meier curves (Kaplan and Meier 1958) will be estimated, and quartiles and rates at various time points together with the 95% CI will be provided. Missing data will not be imputed.

The interpretation of the study results will be the responsibility of the investigator with the Lilly CRP, pharmacokineticist, and statistician. The CRP and statistician will also be responsible for the appropriate conduct of an internal review for both the final study report and any study-related material to be authorized by Lilly for publication.

This study will have 2 database locks. The first database lock will occur when the pre- and post-olatumab monotherapy tissue biopsies and the predose C1D1 and predose C2D1 whole blood samples have been collected for all 35 evaluable patients. The main purpose of this database lock is to assess biomarker expression level changes pre- and post-olatumab monotherapy. The safety of olatumab will also be evaluated at this database lock. The second database lock will occur at the end of the study when all patients have either completed or discontinued from the study and the 30-day short-term follow-up period has been completed. In the second database lock, all of the study objectives will be evaluated. There will be an interim analysis to look at the biomarker data once approximately half of the evaluable patients complete the second biopsy and the predose C2D1 whole blood draw.

10.1.1. Determination of Sample Size

To investigate the primary objective, approximately 35 evaluable patients have to have completed the pre-treatment tissue biopsy, the predose C1D1 whole blood draw, 1 cycle of olatumab monotherapy, the post-olatumab monotherapy biopsy, and the predose C2D1 whole blood draw.

If the patient is noncompliant during olatumab monotherapy (Cycle 1) and does not undergo the pre-treatment tissue biopsy, the post-olatumab monotherapy biopsy, or the predose C1D1 and predose C2D1 whole blood draw, he or she will be considered nonevaluable and may be replaced.

It is hypothesized that 49% (17 out of 35) or more patients will have a reduction of at least 30% in PDGFR α level change in tissue from baseline to post-olatumab monotherapy. The sample size of 35 patients provides a 95% CI that the hit rate (proportion of patients with at least 30% reduction in PDGFR α level change from baseline) will be between 31% and 66%, which excludes a 30% or lower hit rate.

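### The sample-size statement credits 35 patients with a 95% CI of 31%-66% that rules out a 30% hit rate, but this holds only if at least 17 hits are seen, about 59% likely at a true rate of 49%

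*Protocol*

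**What the plan says.** Protocol 10.1.1 requires that "approximately 35 evaluable patients have to have completed the pre-treatment tissue biopsy", together with the paired blood draws, one cycle of olaratumab monotherapy and the second biopsy. It then sets the expectation for PDGFRα in tissue: "It is hypothesized that 49% (17 out of 35) or more patients will have a reduction of at least 30" per cent. A patient with such a reduction is a hit.

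The precision statement follows: "The sample size of 35 patients provides a 95% CI that the hit rate" "will be between 31% and 66" per cent, "which excludes a 30% or lower hit rate". SAP 5.1 carries the same statement.

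Neither document gives a power, a probability of obtaining such an interval, or a CI method for the hit rate. Protocol 10.1 says "The analyses for this study will mostly be descriptive", and SAP 5.2 likewise describes the analyses as descriptive apart from possible exploratory work. For the hit rate itself, Protocol 10.5 and SAP 5.9 plan only a count and a frequency.

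**The concern.** In the precision statement the sample size is what delivers the interval, and the wording carries no condition. A sample size can fix the approximate width of an interval, but not where it lies; that depends on how many hits occur. Whether the interval excludes 30% is therefore an outcome of the trial, with a probability that depends on the true hit rate.

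The hypothesised count of 17 also appears to be the smallest count that excludes 30%. If so, a true rate at the lower edge of the hypothesis puts the expected count on the boundary, and random variation takes the result below it in a large share of trials.

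This is the only quantitative justification for N in either document. A reader may take it as assurance that a true rate of 49% will be distinguished from 30%. If 15 or 16 hits are then seen, a result quite compatible with the hypothesis would look like a shortfall against the plan's own statement.

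**Working it through.** **Inputs** (Protocol 10.1.1, same in SAP 5.1): n = 35 evaluable patients; hypothesised rate 49%, that is 17/35 = 48.57%, or more; 95% level, taken as two-sided because both limits are printed; stated interval 31% to 66%; reference rate 30%.

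**Step 1: reproduce the stated interval.** The exact limits for x hits in n are:
- lower = the 0.025 quantile of Beta(x, n − x + 1)
- upper = the 0.975 quantile of Beta(x + 1, n − x)

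For x = 17 and n = 35, these are Beta(17, 19) and Beta(18, 18), giving 31.4% to 66.0%. Rounded, that is the printed 31% to 66%.

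Other methods for 17/35:

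| Method | 95% CI |
|---|---|
| Exact (Clopper-Pearson) | 31.4% to 66.0% |
| Wald | 32.0% to 65.1% |
| Wald, continuity-corrected | 30.6% to 66.6% |
| Wilson | 33.0% to 64.4% |
| Agresti-Coull | 33.0% to 64.4% |
| Jeffreys | 32.7% to 64.7% |

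Of these, only the exact method rounds to both printed limits.

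**Step 2: find the smallest count that excludes 30%.**

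| Hits of 35 | Exact 95% CI | Excludes 30%? |
|---|---|---|
| 15 | 26.3% to 60.6% | no |
| 16 | 28.8% to 63.4% | no |
| 17 | 31.4% to 66.0% | yes |
| 18 | 34.0% to 68.6% | yes |

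The smallest count is 17, the same as the hypothesised count.

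**Step 3: probability of reaching it.** With X ~ Binomial(35, p), P(X ≥ 17) is the sum over x = 17 to 35 of C(35, x) p^x (1 − p)^(35 − x).

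| True rate p | P(X ≥ 17) |
|---|---|
| 30% | 1.6% |
| 17/35 (48.57%) | 56.6% |
| 49% | 58.6% |
| 50% | 63.2% |
| 54% | 79.2% |
| 55% | 82.5% |
| 60% | 93.8% |

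Solving for p, the probability is 80% at 54.2% and 90% at 57.9%. At a true 49%, the interval fails to exclude 30% with probability 1 − 0.586 = 41.4%.

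**Step 4: sensitivity to the CI method.** With Wilson, Agresti-Coull or Jeffreys limits, 16 hits are enough (lower limits 30.5%, 30.5% and 30.1%). P(X ≥ 16) is then 71.1% at 49% and 69.3% at 17/35. The exclusion is still not assured, and these methods do not give the printed interval.

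**The case against.** The strongest reply is that the paragraph can be read conditionally. The preceding sentence names 17 of 35, so a statistical reader may supply the missing condition: if that result is seen, the interval is 31% to 66%. This is a common way to justify a descriptive sample size, and the printed limits are right for that result. That stands, and it is why the point concerns the wording of the claim and not the calculation. It does not rescue the sentence, which states no condition and adds that 30% is excluded.

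Second, the hypothesis is 49% or more, so 59% is the lowest value over the hypothesised range. This also stands, and the figure should always be quoted as the value at that edge. But 49% is the only rate the plan names, and the probability reaches 80% only about five points higher.

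Third, the CI method is not stated for the hit rate. The exact method is an inference, supported by the match in both limits and by the exact intervals that SAP 5.10 plans for ORR and DCR. Under Wilson-type limits the figure would be about 71%, so the size of the gap depends on the method, but its existence does not.

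A reader might go further and infer that the trial is underpowered, that N must rise, or that 16 or fewer hits would mean a failed primary endpoint. The documents do not support this. They claim no power, specify no test of 30%, and make no action depend on the interval. The interim analysis in SAP 5.14 looks for technical problems with the assays and reviews safety; it has no hit-rate threshold. PDGFRα is also only one of several primary biomarkers, beside CTC counts, PDGFRβ and the four ligands.

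**Conclusion.** The statement is wrong as written: it gives the sample size a property that the design does not have. The interval of 31% to 66% is correct for 17 hits in 35, and only for that result. Exclusion of 30% requires at least 17 hits, which has a probability of about 59% at a true rate of 49%.

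This is an overstated precision claim in a descriptive plan. It is neither an arithmetic error nor a wrong power figure, and it gives no ground for changing N.

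The 59% rests on three assumptions: exact two-sided 95% limits, independent patients with a common hit probability, and exactly 35 patients evaluable for PDGFRα. The plan says approximately 35, so the probability will shift somewhat if the final number differs.

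**What to change.** Replace the precision sentence in Protocol 10.1.1 and SAP 5.1 with wording such as:

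> If 17 of 35 evaluable patients are hits, the exact 95% CI is 31% to 66%. At least 17 hits are needed for the exact CI to exclude 30%. With 35 evaluable patients the probability of this is about 59% if the true rate is 49%, and about 80% if it is about 54%.

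This also names the CI method, which is currently left to inference. If the sponsor prefers to state no probabilities in a descriptive plan, the minimum correction is to make the interval conditional on 17 of 35 and drop the unconditional claim about 30%.

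The change is a few sentences in each document. Sample size, endpoints, analyses and conduct are unaffected. The cost is that the stated assurance becomes less favourable than the present text suggests.

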10.1.2. Analysis Populations

Efficacy analysis: the efficacy analysis will be performed on the intent-to-treat (ITT) population, which includes all enrolled patients. The ITT population will be included in overall patient listings, in summary tables of patient demographics and disease characteristics, in the list of treatment discontinuation after enrollment, and in the analysis of efficacy.

Safety analysis: all enrolled patients who receive any quantity of IP, regardless of their eligibility for the study, will be included in the safety analysis. Safety evaluation will be performed based on the actual therapy a patient has received.

Biomarker analysis: the biomarker evaluable 1 (BE1) population will include all ITT patients with evaluable samples at both baseline and post-olatumab monotherapy. The BE1 population will be used in the biomarker analyses for the primary objective and exploratory objectives. The biomarker evaluable 2 (BE2) population will include all ITT population with evaluable samples at both baseline and post-combination (olatumab plus doxorubicin) therapy, and will be used in the biomarker analyses for the exploratory objectives.

